A randomization list will be generated by study biostatistician and will be stratified by sex. This provides an assignment that the study staff has no control over the randomization process and that each participant has an equal chance of being assigned to either group. These group assignments will be pre-specified and placed in sealed envelopes unmarked except for an envelope number (TEMPO1## or TEMPO2##) on the outside. Envelopes with numbers starting with the number 1 (e.g., TEMPO1##) will be for male participants and those starting with the number 2 TEMPO 2## will be for female participants. For participants who opted-in for the in-person baseline visit, the randomization procedures will occur inperson after the baseline data collection procedures have been completed.

Below is a script that the research assistant will use for the randomization procedures

4d. Post-Intervention (Week 8) Visit

The weekly attendance of the participants will be tracked on an Attendance Survey on REDCap. The completion of the 8th session will trigger the ASI for the post-intervention remote surveys. Participants will receive a total of 15 surveys, including self-reported pain, function, and psychological measures collected at baseline and feedback and satisfaction surveys. Those who opted in for the in-person baseline visit will be invited for the in-person post-intervention visit.

4e. Follow-up (Week 14) Surveys

Six weeks after the end of the 8-week intervention, participants will be administered six surveys related to their knee pain, function, perceived impression of change, and psychological measures.

4f. Weekly (Week 1-14) Surveys

All participants will be administered a short weekly survey starting from the start of the intervention (week 1) to the follow-up period (week 14). This weekly survey will include a question related to pain in a specific activity selected at baseline and will also include home exercise, physical activity, and medication log. For those assigned to the mindful exercise group, additional questions related to mindfulness and mindful exercise log will be included. The weekly survey will be administered by email using automated survey reminders in REDCap.

4g. Individual Interviews (Week 8)

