At the end of the 8-week interventions, participants from the mindful exercise intervention will be invited for individual interviews. The interviews will be conducted over Zoom by a professor who is an expert in qualitative methods and who was not involved in any other study procedures. The interview guide will be theoretically informed based on the Theoretical Framework of Acceptability(1). The interviews will be audio-recorded on Zoom and transcribed verbatim and de-identified by GMR transcription services in Boston.

5. Interventions Description, Overview, Objectives

5a. General Overview

Two days before the first intervention session, participants will receive a reminder email informing them of the date, time, and zoom link of the intervention session. This information will also be provided in the manual given to them at the baseline visit. One day before the intervention session, participants will receive a call from the research assistant reminding them of the first intervention session.

Participants in both groups will receive 8 telehealth, group-based, supervised intervention sessions. Participants in the exercise group will receive evidence-based strengthening and neuromuscular exercises for the knee for 12-weeks. Participants in the mindful exercise group will receive the same exercises but they will be trained on performing the exercises mindfully. The interventions will be conducted in two waves.

5b. Interventions

Interventions will be delivered in a group setting in two waves over 8-weeks. Once at least 12 people are recruited, interventions for wave 1 will commence. Recruitment and randomization processes will be ongoing while interventions for wave 1 participants are in progress. Once 40 participants are randomized, recruitment will cease and the interventions for the second wave of participants will commence.

[figure not shown]
Interventions in both mindful exercise and exercise groups will be delivered in a group setting via HIPAA-protected Zoom videoconferencing software. Along with the interventions below, participants in both groups will receive educational materials each week via email (Table 5), a program manual that contained information about study tasks and interventions, and a set of resistance bands and a step-up platform with adjustable height. After the end of the 8-week interventions, participants were asked to continue to practice on their own for another 6 weeks.

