Adverse event (AE) is any unfavorable or unintended diagnosis, sign (including abnormal laboratory finding), symptom, or diseases temporarily associated with the study intervention, which may or may not be related to the intervention. AEs include any new events not present during the pre-intervention period or events that were present during the pre-intervention period but have increased in severity.

Serious adverse event (SAE) is any AE that results in any of the following outcomes:

- Death,
- Life-threatening adverse experience,
- Inpatient hospitalization or prolongation of existing hospitalization,
- Persistent or significant disability/incapacity,
- Congenital anomaly/birth defect, or cancer, or any other experience that suggests a significant hazard, contraindication, side effect or precaution that may require medical or surgical intervention to prevent one of the outcomes listed above,
- Event that changes the risk/benefit ratio of the study.

An unanticipated problem is any incident, experience, or outcome that meets ALL of the following criteria:

- Unexpected in terms of nature, severity, and frequency, given the research procedures that are described in the protocol related documents the characteristics of the subject population being studied
- Related or possibly related to a subjects participation in the research study, and
- Suggests that the research places subjects or others at a greater risk of harm (including physical, psychological, economic, or social harm) related to the research than was previously known or recognized.

8a. Event Notification

The clinical tests used in this study offer minimal risks to participants and will be administered by an experienced team in working with this patient population. Participants will be asked if any events have occurred prior to each intervention or testing session and to report all activity-related symptoms of pain or discomfort to the investigator or research team member, who will decide if medical care is warranted, and arrange for that care as appropriate. Participants will be constantly supervised and assisted as necessary throughout their testing and training session.

Because this study's procedures pose relatively low risk to participants, weekly data and procedural reviews by the PI in consultation with study staff will be sufficient to identify and ameliorate any potential safety issues.

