Any safety concerns about the exercise or clinical protocol will be brought to the immediate attention of the PI. Study staff will report non-serious AEs to the PIs within 7 days.

Study staff will report SAEs to the PI and the research assistant as soon as they are made aware of the SAE. All research personnel who have contact with study participants are responsible for reporting to appropriate study personnel all events directly observed or reported by the study participant. When necessary, additional details of an event should be obtained by the participant's outside/personal clinician or PCP.

Once the PI and research assistants are notified of the event, the following steps will be taken:

- 1. The PI will determine if the event is a SAE or an event or problem that is unanticipated (in terms of nature, severity, or frequency, related or possibly relate) and suggest that there is an increased risk to subjects or others than was previously known
- 2. If the event is an SAE refer to section 8a.1
- 3. If the event or problem is unanticipated and meets all of the above criteria (unexpected, related to the study, and increases risk) refer to section 8a.2
- 4. For all events or problems, the research assistants will begin the AE/SAE form under the appropriate participant and fill in the relevant information. This form should be completed once the research assistant is made aware of the event and more information can be completed as the event unfolds. The information from this form can be used in the report to IRB when appropriate.

5. The PI is responsible for making the final decision regarding attribution of the AE to study and the severity of the AE (mild, moderate, or severe).

8a.1. Reporting to IRB

The IRB is responsible for ensuring compliance with federal regulations and state laws for the protection of the rights and welfare of human research participants. The following events must be reported to the IRB within 5 working days of discovery:

- 1. Death of a research subject if the death is related or possibly related to the research study.
- 2. Adverse events that are unanticipated (in terms of nature, severity, or frequency, related or possibly related, and suggest that there is an increased risk to subjects or others than was previously known.

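### The only scheduled adverse event question in the readable text comes before sessions, so weeks 9-14 and anyone who stops attending rely on spontaneous reporting of activity-related symptoms.

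*Combined protocol and SAP*

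**What the plan says.** **Scheduled enquiry.** Section 8a (Event Notification) states: "Participants will be asked if any events have occurred prior to each intervention or testing session". The sentence goes on to ask participants "and to report all activity-related symptoms of pain or discomfort to the investigator or research team member". Section 8b repeats the request about activity-related symptoms.

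**Staff duty.** Also in 8a, research personnel in contact with participants are "responsible for reporting to appropriate study personnel all events directly observed or reported by the study participant". Under 8a.2, interventionists notify the team of events involving the interventions.

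**Contacts over time.** Section 5a: "Participants in both groups will receive 8 telehealth, group-based, supervised intervention sessions". Section 5b adds that after the eight weeks "participants were asked to continue to practice on their own for another 6 weeks". Section 4f sends a weekly emailed survey to everyone in weeks 1 to 14. It carries a question on pain in a nominated activity and "will also include home exercise, physical activity, and medication log", plus mindfulness items in one arm. At week 14, Section 4e says "participants will be administered six surveys related to their knee pain, function, perceived impression of change, and psychological measures".

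**Definition and use.** Section 8 defines an AE as any untoward diagnosis, sign, symptom or illness during the intervention, related to it or not. Section 7 reports the number of safety events descriptively, with no collection window or denominator.

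**The concern.** The count of safety events is a planned result of a trial testing a new combined program. As described, the prompt for that count is attached to attendance. Someone who stops coming, perhaps because of a flare, is no longer asked, and nobody is asked routinely while practising unsupervised. A fall at home, a hospital admission or a new diagnosis in weeks 9-14 would meet the AE definition, yet falls outside what participants are told to volunteer.

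If stopping differed by arm, the number of prompts would differ too. Sessions last one hour in the exercise arm and about two in the mindful exercise arm, so this is plausible, but the documents contain no data on it. A reader of the results could not tell whether a low count reflects few events or few questions.

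**Working it through.** The plan states no event rate, expected count or expected attendance, so there is no figure of its own to reproduce. The check sets the reporting routes against the calendar.

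**Inputs**
- Eight weekly sessions, weeks 1-8 (Section 5a, Table 1).
- Unsupervised practice for six weeks, weeks 9-14 (Section 5b).
- Follow-up of 14 weeks (Section 4f, Table 1). Section 4 elsewhere calls the study 18 weeks long; I use 14 because 4f and Table 1 agree.
- Testing sessions: the only ones described are the optional in-person visits before and after treatment. I do not count emailed surveys as testing sessions.
- Attendance: not given, so the values below are assumptions.

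**Step 1. Routes by period**

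| Route | Weeks 1-8 | Weeks 9-14 |
|---|---|---|
| Scheduled AE question (8a) | Before each attended session | None readable, apart from any optional post-treatment visit |
| Participant volunteers (8a, 8b) | Activity-related symptoms | Activity-related symptoms |
| Staff pass on what they see or are told (8a) | Sessions and other contacts | Little to observe without sessions |
| Weekly survey (4f) | Pain, exercise, activity, medication | Same; no event item listed |

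**Step 2. Weeks after the last session**

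(14 - 8)/14 = 6/14 = 42.9%.

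**Step 3. Occasional missed sessions**

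Section 8a sets no recall limit, so an event missed one week can be picked up at the next attended session. Assume sessions are attended independently with probability p, and that an event in week w is asked about if any session from w to 8 is attended. Its chance of being prompted is 1 - (1 - p)^(9 - w). Averaging over w = 1 to 8:

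| p | Share of weeks 1-8 covered |
|---|---|
| 90% | 98.6% |
| 80% | 96.9% |
| 70% | 94.6% |
| 50% | 87.5% |

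With 70% attendance in one arm and 90% in the other, the ratio of coverage in weeks 1-8 is 94.6/98.6 = 0.96. Missed sessions alone matter little. The convention slightly favours the plan, because it treats each event as preceding that week's session.

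**Step 4. Permanent stopping**

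If the last attended session is k, and there is no later in-person visit, the share of the 14 weeks with no later prompt is (14 - k)/14:

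| Last session k | Calculation | Share |
|---|---|---|
| 2 | 12/14 | 85.7% |
| 4 | 10/14 | 71.4% |
| 6 | 8/14 | 57.1% |
| 8 | 6/14 | 42.9% |

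The gap therefore lies in early stopping and in weeks 9-14, not in occasional absence.

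**The case against.** Four arguments run the other way.

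1. **Reporting does not end with the sessions.** A reader might infer that AE capture stops at week 8. The text does not support that: the self-report request and the staff duty have no end date and do not depend on attendance. This stands, and the correct description is that reporting becomes spontaneous. But the request names only activity-related pain or discomfort, and the staff duty covers only what is seen or told.

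2. **Table 1 may hold a scheduled collection.** Its key defines AE/SAE, several row labels are unreadable, and the table of email and telephone contacts announced in Section 2b cannot be found. A tick at week 8 or week 14 would itself be scheduled collection. This stands, so I do not claim that none exists. A single week 14 enquiry would still mean up to six weeks of recall from those who respond, and would not supply the window missing from Section 7.

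3. **Non-attenders are still asked about pain.** The weekly survey goes to everyone, asks about activity pain and medication, and treatment history is repeated at weeks 8 and 14. Some flares would be visible there. The documents do not say, however, that such answers are reviewed or recorded as AEs. The investigator's data review, weekly in 8a and monthly in 8b, can only work on what was collected.

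4. **The count is descriptive.** Safety is not one of the three listed feasibility outcomes, and no between-arm event rate is planned. A reader might infer that unequal attendance distorts the arm comparison in direct proportion. That would need a one-week recall limit the plan never states; Step 3 shows a far smaller effect without one. This argument limits the priority of the point but does not remove it.

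**Conclusion.** The point holds as a gap in how AE ascertainment is described, with an inexpensive remedy; it is not a numerical error. On the readable text, prompted collection covers the weeks up to a participant's last attended session, plus any optional in-person visit. Everything later, including 6 of 14 weeks (42.9%) for full attenders with no such visit, rests on volunteered reports with a scope narrower than the AE definition. For someone who stops at session 2, 4 or 6 and makes no in-person visit, the unprompted share is 85.7%, 71.4% or 57.1%.

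These figures are shares of calendar time, not of events lost. How many events would be missed, and whether the arms would differ, cannot be estimated from the documents. The conclusion assumes that no unreadable schedule row provides further AE collection and that emailed surveys are not testing sessions. If a row does exist, the gap narrows for the visits it covers.

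**What to change.** **Section 4f.** Add one event question, identical in both arms, to the REDCap survey in weeks 1-14. It should ask about any new or worse health problem, injury or medical visit. Asking about the time since the last completed survey means that a skipped survey delays the answer rather than losing it. Table 4 describes the weekly survey as running during treatment only, and should be aligned with 4f.

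**Section 8a.** State that this question is a scheduled source of AEs alongside the pre-session enquiry. Make clear in the body text any AE collection that Table 1 schedules.

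**Section 7.** State the collection window (weeks 1-14). Report events by arm and by period (weeks 1-8 and 9-14), show prompted and spontaneous events separately, and give the number of surveys returned in each arm and period.

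**Cost.** One item on a survey already sent, and more minor events to log. Ascertainment will then depend partly on survey response, which is why the number returned should be shown beside the counts.

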Mindful Exercise Program					X	X	X	X	X	X	X	X		
Attendance to sessions					X	X	X	X	X	X	X	X		
Weekly Surveys					X	X	X	X	X	X	X	X	X	X
HEAL Treatment Expectancy				X										
eHEALS				X										
A-REALM				X										
Demographics			X											
Knee OA history			X											
Treatment History			X											
Treatment History – follow-up												X		X
Comorbidity			X											
Access to health technology			X											
PHQ-8			X									X		X
ASES			X									X		
PEG			X									X		X

WPI		X									X		
Catastrophizing		X									X		
Homunculus		X									X		
PainDETECT		X									X		
		X									X		X
		X											
- Follow-up											X		X
R		X									X		X
A		X									X		X
PA		X									X		
		X									X		
											X		X
k survey											X		
											X		
tion Scale											X		
al interviews											X		
	Catastrophizing Homunculus PainDETECT Follow-up R A PA k survey	Catastrophizing Homunculus PainDETECT Follow-up R A PA Lion Scale	Catastrophizing X Homunculus X PainDETECT X X X Follow-up R X X X X X X A X X X X A X X	Catastrophizing X Homunculus X PainDETECT X X - Follow-up R X X A X X A X X A A	Catastrophizing X Homunculus X PainDETECT X X Follow-up R X X A X X A X A X A X A X A X A X A X A X A X A X A X A X A A	Catastrophizing X Homunculus X PainDETECT X X X -Follow-up R X X A X X A A	Catastrophizing X Homunculus X PainDETECT X X -Follow-up R X X A X X A A	Catastrophizing X Homunculus X PainDETECT X X X -Follow-up R X X A X X A X A X A X A X A X A X A X A X A X A X A X A A	Catastrophizing X	Catastrophizing X Homunculus X PainDETECT X X X -Follow-up R X X X X X X X X X X X X	Catastrophizing X Homunculus X PainDETECT X X X -Follow-up R X X X X X X X X X X X X	Catastrophizing X Homunculus X PainDETECT X X X S X Follow-up X X X	Catastrophizing X Homunculus X PainDETECT X X X Follow-up X X X

BV-R: Remote Baseline Visit

RTT: Remote Randomization and Telehealth Training Visit

W8-R: Remote Post-intervention Visit

W14: Remote Follow-up Visit

BMI = Body Mass Index

eHEALS = ehealth Literacy Questionnaire

A-REALM = Arthritis-Adapted Rapid Estimate of Adult Literacy in Medicine

PHQ-8 = 8-item Patient Health Questionnaire

ASES = Arthritis Self-Efficacy Scale

PEG = Pain Enjoyment General Activity Survey

WPI = Widespread Pain Index

KOOS = Knee Injury and Osteoarthritis Outcome Score

NRSna = Numeric Rating Scale for nominated activity

PROMIS Sleep = Patient-Reported Outcomes Information System measuring sleep quality and sleep disturbance

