Exercise Progressions: All participants will be expected to monitor their own progressions. For this, information regarding the appropriate intensity of exercise (4-6 range on the Modified Borg's RPE Scale)¹¹⁷ will be provided to them in their home exercise manuals. During the exercise sessions, participants will be given options (and shown video demonstration of options) for making the exercise easier or more challenging so that they can stay within the range of 4-6 on the RPE scale. During the intervention sessions, the participant will be given constant reminders of the desired exercise intensity and the interventionist will answer any questions the participant might have regarding their level of exercise performance.

5b.2. Mindful Exercise Sessions

The mindful exercise intervention will be delivered jointly by a physical therapist (NS) and a mindfulness instructor with ~ 20 years of experience. Along with the exercises, participants in the mindful exercise group will training in mindfulness in the first 3 sessions (Table 7). Starting from session 4, participants will be instructed to integrate mindfulness into their exercise movements. Each session will be ~ 2 hours in length roughly divided into four 30-min blocks. In the first and third 30-min blocks, participants will practice concepts of mindfulness meditation wherein they will be trained to develop non-judgmental moment-to-moment awareness using either breath, body sensations, or counting as an anchor. In the second and the fourth 30-min blocks, participants will perform the same exercises as those provided to the exercise group. However, participants in this group will perform the exercises mindfully, i.e., they will use either breath, body sensation, or counting as an anchor while performing exercise movements. Participants in this group will receive same instructions as the exercise group for home exercise. Furthermore, participants in this group will be advised to practice mindfulness for at least 20-minutes each day and to practice mindfulness during exercise and physical activity.

Table 7: Meditations in the Mindful Exercise program

Sessions and Goals	Meditations			
	Session 1			
Raisin meditation	Training on how to separate senses of observation, touch,			
	sound, and feel			
Awareness of breath meditation	Training on how to use breath as an anchor			
	Session 2			
Body scan meditation	Training on how to use body sensation as an anchor			

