Breath and counting meditation Training on how to use counting as an anchor				
	Session 3			
Moving meditation	Introducing how to combine movement and mindfulness			
Body scan meditation	Practice on how to use body sensation as an anchor			
Mindful exercises	Combining exercise and mindfulness			
Session 4				
Breath and counting meditation	Training on how to exercise using either the breath, counting,			
C	or body sensation as an anchor			
Walking meditation	Combining movement and mindfulness			

Mindful exercises	Combining exercise and mindfulness				
Session 5					
Awareness of breath meditation	Practice on how to use breath as an anchor				
Mindful exercises	Combining exercise and mindfulness				
	Session 6				
Awareness of breath meditation	Practice on how to use breath as an anchor				
Body scan meditation	Practice on how to use body sensation as an anchor				
Mindful exercises	Combining exercise and mindfulness				
	Session 7				
S.T.O.P meditation	Training on incorporating mindfulness in daily life				
(S=sit down, T=take a breath,					
O=observe, P=proceed with day)					
Pain-focused meditation	Training on how to detach from difficult sensations				
Mindful exercises	Combining exercise and mindfulness				
	Session 8				
Review and summary	A summary and practice of what was covered in the 8-week				
	program and practice of aware of breath and body scan				
	meditations				
Mindful exercises	Combining exercise and mindfulness				

7. Statistical Analysis Plan

The following outcome measures will be used to determine feasibility of the telehealth interventions in this study.

- a) Recruitment: Proportion of participants successfully contacted who agreed to participate in the study over 6-months
- b) Attendance: Proportion of sessions attended
- c) Retention: The percentage of participants who complete the post-intervention surveys at the end of the study period (12-weeks)

The number of safety events, and data for recruitment, attendance, and retention will be reported descriptively. Aggregate data for intervention adherence at home as well as feedback from the participants will be reported. For other PROs, within group changes and differences between groups along with 95% confidence intervals will be reported. Data will be reported using an intention-to-treat approach with data from all randomized participants included. Missing data will not imputed.

8. Safety Reporting

AEs, SAEs, and Unanticipated Problems Definitions

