The clinical tests used in this study offer minimal risks to participants and will be administered by an experienced team in working with this patient population. Participants will be asked to report all activity- related symptoms of pain or

discomfort to the investigator, who will decide if medical care is warranted, and arrange for that care as appropriate. Participants will be constantly supervised and assisted as necessary throughout their testing and training session. Trained research assistants will perform sensor placement and monitor participants during the experimented procedures. The research procedures in this study are relatively low risk to participants; monthly data and procedural reviews by the PI in consultation with study staff will be sufficient to identify and ameliorate any potential safety issues. Any safety concerns about the exercise or clinical protocol will be brought to the immediate attention of the PI.

8c. Protocol Deviation

This section of the MOOP describes relevant deviations/violations and the reporting process to appropriate parties. Deviation is defined as any change or alteration to the IRB-approved protocol without prospective IRB approval. A protocol deviation is any occurrence that is not in compliance with the approved study protocol, IRB policies, federal regulations, or any other applicable regulations.

Major Deviation

Major Deviation is defined as any change or alteration that has the potential to:

- Adversely affect the rights, welfare or safety of the participants,
- Adversely affect the integrity of the research data, or
- Affect the participant's willingness to participate.

Major deviations should be reported to the IRB within 5 working days.

Minor Deviation

Minor Deviation is defined as any change or alteration that has not or does not have the potential to:

- Adversely affect the rights, welfare or safety of the participants,
- Adversely affect the integrity of the research data, or
- Affect the participant's willingness to participate in the study.

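### The only symptoms participants are specifically told to report, and the immediate-attention sentence, do not name mindfulness, so non-serious psychological events are likely to be captured less completely than exercise-related pain

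*Combined protocol and SAP*

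**What the plan says.** **Ascertainment.** Section 8a opens with a general query: "Participants will be asked if any events have occurred prior to each intervention or testing session". The same sentence then asks participants "to report all activity-related symptoms of pain or discomfort to the investigator or research team member". Section 8b, on monitoring, carries over only the second part ("Participants will be asked to report all activity- related symptoms of pain or" discomfort) and leaves out the general query.

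**Escalation.** Both 8a and 8b state: "Any safety concerns about the exercise or clinical protocol will be brought to the immediate attention of the PI". Elsewhere in 8a, serious events of any cause go to the PI as soon as staff know of them, and non-serious events within 7 days. All staff in contact with participants must pass on events they observe or are told about. Section 8a.2 requires interventionists to notify the study team of events in either intervention, and names both.

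**Definitions.** An adverse event is any unfavourable symptom, related or not, including a worsening of something already present. The unanticipated-problem definition refers to a "greater risk of harm (including physical, psychological, economic, or social harm").

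**What separates the arms.** Under Section 5b.2 both arms do the same exercises. The mindful arm adds two 30-minute meditation blocks per session and is "advised to practice mindfulness for at least 20-minutes each day". Session 7 in Table 7 includes a pain-focused meditation, described as "Training on how to detach from difficult sensations".

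**Reporting.** Section 7 reports the number of safety events descriptively and mentions no split by type.

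**The concern.** The experimental component is mindfulness, and Section 8 itself recognises psychological harm. Yet the one class of symptom that participants are told to report belongs to the component that both arms share. Exercise-related pain gets an open question plus a named instruction. Distress, anxiety or low mood linked to meditation gets the open question and staff observation only. A participant who has been told to report activity-related pain may not think of distress during home meditation as an event worth mentioning.

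Two things are at stake. First, the safety count may under-represent the type of event on which the arms could differ most, in a feasibility study that is meant to precede an effectiveness trial. Second, a non-serious concern about the mindfulness content is not clearly covered by the sentence that promises immediate attention.

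**Working it through.** The plan states no figure on this point, so there is none to reproduce. The main check is a comparison of wording.

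**Step 1: routes by which an event can reach the record**

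| Route | Exercise-related pain | Meditation-related distress |
|---|---|---|
| Open question before each session (8a) | Yes | Yes |
| Named symptom instruction (8a, 8b) | Yes | No |
| Staff duty to report observed or reported events (8a) | Yes | Yes |
| Interventionist notification (8a.2) | Yes | Yes |
| Serious events at once; non-serious within 7 days (8a) | Yes | Yes |
| Immediate-attention sentence (8a, 8b) | Named | Not named |

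The two columns differ in two rows. That is the extent of the gap. It is wider if 8b is read alone, because the open question is missing there.

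**Step 2: exposure to the unnamed component.** Inputs are from Section 5b.2.
- In session: 8 sessions × 2 blocks × 30 min = 8 h.
- At home over 8 weeks: 20 min × 7 days × 8 weeks ÷ 60 = 18.7 h.
- Total: 8 + 18.7 = 26.7 h per participant. About 70% of it (18.7 ÷ 26.7) is at home, where staff observation cannot help.

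**Step 3: illustration of what incomplete capture does.** The number of participants follows from the protocol: 40 randomised with equal chance gives about 20 in the mindful arm. The event rate r and the captured share d are assumptions, because the documents give neither.

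P(at least one recorded) = 1 − (1 − r·d)^20

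| r | d = 1 | d = 0.5 | d = 0.3 |
|---|---|---|---|
| 10% | 1 − 0.90^20 = 88% | 1 − 0.95^20 = 64% | 1 − 0.97^20 = 46% |
| 5% | 1 − 0.95^20 = 64% | 1 − 0.975^20 = 40% | 1 − 0.985^20 = 26% |

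If no event is recorded, the one-sided 95% upper limit on the recorded rate is 1 − 0.05^(1/20) = 13.9%. The matching limit on the true rate is 13.9% ÷ d: about 28% at d = 0.5 and 46% at d = 0.3.

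**Step 4: after week 8.** Section 5b asks participants to continue on their own for 6 more weeks. The session-linked question then stops, and Section 4f describes a weekly survey of pain and logs with no adverse-event item. This applies to both arms. It is uncertain, because some row labels of Table 1 are unreadable in the available text and its key lists AE/SAE.

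**The case against.** A reader might infer from the narrow instruction that harm from mindfulness is found only if participants volunteer it. The documents contradict that. Staff ask about events of any kind before each session in both arms, staff must report what they observe, and a mindfulness instructor co-delivers the sessions of the mindful arm. A reader might also infer that mindfulness-related events have no escalation route. That fails too: serious events go to the PI at once and non-serious ones within 7 days whatever the cause, 8a.2 names the mindful exercise intervention, and the clinical protocol could be read to include mindfulness.

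Other points on that side have weight:
- Open questioning applied equally to both arms is a coherent method.
- PHQ-8, mindful-arm interviews and participant feedback give further information on mood and acceptability. They are not adverse-event ascertainment, though, and the interviews exist in one arm only.
- The fields of the REDCap adverse-event form are not shown, so a structured or typed item may already exist.
- Section 7 makes no safety claim and sets no safety criterion. Even with full capture, no events among 20 participants leaves an upper limit of 13.9%, so this trial could not establish safety in any case.

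These points limit the concern to non-serious events and to completeness of capture. They do not remove the two rows in which the columns differ, or explain why 8b drops the open question and why 8a and 8b are worded more narrowly than 8a.2.

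**Conclusion.** The concern holds in a limited form. The one specific reporting instruction covers activity-related pain or discomfort, and the immediate-attention sentence omits the component under test. Non-serious psychological events from meditation are therefore likely to be captured less completely than exercise-related pain in the Section 7 count. Serious events are not affected, and no class of event lacks an escalation route.

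The size is not known. The probabilities above show direction only; they rest on assumed event rates of 5% and 10%, assumed capture of 30% to 100%, and 20 participants in the mindful arm. Full capture under a directed prompt is an assumption too. The change is worth making because it is cheap and improves detection for the component that separates the arms. Confidence is medium, because the adverse-event form and part of Table 1 cannot be seen.

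**What to change.** 1. In 8a and 8b, replace the activity-related wording with one neutral prompt, identical in both arms: *any physical or psychological symptom (including distress, anxiety or low mood) during or after exercise or mindfulness practice*.
2. Repeat the open question about events in 8b, so that the two sections agree.
3. Change the immediate-attention sentence in both sections to cover *the exercise, mindfulness or clinical protocol*, in line with 8a.2.
4. In Section 7, report event counts by type (musculoskeletal, psychological, other) and by arm. Add a type code to the REDCap adverse-event form if it has none.
5. Optionally, add a descriptive count per arm of participants whose PHQ-8 ("PHQ-8 = 8-item Patient Health Questionnaire", collected at baseline, week 8 and week 14) worsens beyond a cut-off fixed before any data are seen.

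The cost is wording in two sections, possibly one code on an existing form, and a table line or two. The downside is a somewhat larger number of recorded events, mostly mild, in both arms. Identical wording in the two arms guards against the prompt itself creating a difference between them.
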